10.1.4.1. Statistical Methodology Specification**Model Specification**

- To model the dose-response relationship, a frequentist simplified Emax model is planned. This model assumes the following form:

$$\Delta VL = \frac{(Emax)}{1 + \left(\frac{ED50}{Dose}\right)} + \epsilon$$

Where:

- ΔVL is the change from baseline, defined as Log10 Maximum change from baseline to Day 8 and change from baseline to Day 8 (both parts) in plasma HIV-1 RNA on log10 scale.
- Emax is the maximum response
- ED50 is the dose that attains the 50% of the maximal effect ϵ is a random error assumed to be normally distributed with mean zero and constant variance (σ^2)

The observed maximum change from baseline in Plasma HIV-1 RNA will be used as the response variable in the Emax model.

- The derived data from this Emax model (estimates Emax, ED50 and Variance along with their standard error, and 95% CI) will be tabulated and a dose-response curve will also be produced.
- If problems are encountered Emax model or if the Emax shape is a poor fit for the data and a linear relationship looks plausible across the dose range, then a linear model will be considered of the form:

$$\Delta VL = \alpha * Dose + \epsilon$$

Model Checking & Diagnostics

- Model assumptions will be applied, but appropriate adjustments may be made based on the data.

Model Results Presentation

- The statistical model will use doses from both parts for model fitting.
- The derived data from this Emax model (estimates Emax, ED50 and Variance along with their standard error, and 95% CI) will be tabulated and an exposure-response curve will also be produced.

Example SAS Code:

```
PROC NLMIXED;
PARMS E0 = EST EMAX = EST ED50 = EST S2E = SE;
BOUNDS E0>0 EMAX>0 ED50>0 S2E>0;
PRED = E0 +(EMAX-E0)/(1+(ED50/DOSE));
MODEL RESPONSE ~ NORMAL (PRED, S2E);
PREDICT PRED OUT=DOSE;
RUN;
```

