2.4. Statistical Hypotheses / Statistical Analyses

Study 208132 is a proof of concept (POC), randomized double blind (Sponsor-unblinded) study to characterize antiviral activity, safety/tolerability, PK, and the relationship between PK and antiviral activity of GSK3640254 given once daily (QD), administered across a range of doses over 10 days in Part 1 and over 7 days in Part 2 in HIV-1 infected treatment naïve adults. No formal hypotheses will be tested.

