7.1.3.1. Statistical Methodology Specification

Endpoint / Variables

 Change from baseline to the nadir in Plasma HIV-1 RNA (on log₁₀ scale) Change from baseline to Visit 6 (Day 11 in Part 1 and Day 8 in Part 2) in Plasma HIV-1 RNA (on log₁₀ scale)
Model Specification

 Plasma HIV-1 RNA change from baseline (on log₁₀ scale) to nadir and change from baseline to Visit 6 (Day 11 in Part 1 or Day 8 in Part 2) (on log₁₀ scale) will be fitted in a mixed-effects linear model by treatment, with baseline plasma HIV-1 RNA (on log₁₀ scale) and visit fitted as fixed effects and subject fitted as a random effect.
Model Checking & Diagnostics

 Model assumptions will be applied, but appropriate adjustments may be made based on the data.
Model Results Presentation

 Statistical analysis for maximum change from baseline to the nadir and change from baseline will be presented in tabular format. The linear model will be used to estimate slope, intercept and a 90% CI of the slope. The model will be fitted for Part 1 and Part 2 data respectively. 
Example SAS Code:
 <pre>proc mixed data=dataset; class dose visit subjid; model chgRNA = baseRNA visit dose; random subjid / type=un solution; run;</pre>
Sensitivity and Supportive Analyses
Both ITT and PP population will be used for the above analyses if PP population is differed from ITT population.

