10. PHARMACODYNAMIC ANALYSES

10.1. Primary Pharmacodynamic Analyses

Relationships between dose and PD measures (maximum change (in Day 1 to Day 8) in log₁₀ plasma HIV-1 RNA from baseline) will be explored with an Emax and linear models. Part 1 and Part 2 doses combined in the model fitting. Model selection will be based on Akaike Information Criteria (AIC) value, where model with the lowest AIC value will be considered the best model.

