11.1.3. Statistical Methodology Specification

Endpoint / Variables

 Log₁₀ maximum change from baseline to day 8 in plasma RNA, Log₁₀ change from baseline to Day 8 in plasma HIV-1 RNA relative to the PK parameters (AUC(0-τ), C_{max} and C_{τ}) Day 8/9/10 from Part 1 and Day 7 from Part 2
Model Specification

 To model the exposure-response relationship, a frequentist three-parameter E_{max} model is planned. This model assumes the following form $\Delta VL = E0 + \frac{Emax}{1 + \left(\frac{EC50}{PK}\right)} + \epsilon$ 
Where:
 
 ΔVL is the log₁₀ maximum viral load change from baseline to day 8 or change to Day 8 in plasma HIV-1 RNA E0 is the baseline response Emax is the maximum response

CONFIDENTIAL

208132

- EC50 is the corresponding exposure/PK parameter value that attains the 50% of the maximal effect
- PK is the PK parameter
- ϵ is a random error assumed to be normally distributed with mean zero and constant variance (σ^2)
- If problems are encountered Emax model or if the Emax shape is a poor fit for the data and a linear relationship looks plausible across the dose range, then a linear model will be considered of the form:

$$\Delta VL = \alpha * PK + \epsilon$$

Model Checking & Diagnostics

- Model assumptions will be applied, but appropriate adjustments may be made based on the data.

Model Results Presentation

- The derived data from this Emax model (estimates E0, Emax, EC50 and Variance along with their standard error, and 95% CI) will be tabulated and an exposure-response curve will also be produced. If E0 turns out as not significant, the reduced Emax model without baseline E0 will be selected as the final model.

Example SAS Code:

```
PROC NLMIXED;
PARMS E0 = EST EMAX = EST EC50 = EST S2E = SE;
BOUNDS E0>0 EMAX>0 EC50>0 S2E>0;
PRED = E0 +(EMAX-E0)/(1+(EC50/PARAM));
MODEL RESPONSE ~ NORMAL (PRED, S2E);
PREDICT PRED OUT=DOSE;
RUN;
```

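### The pooled Emax models leave out baseline HIV-1 RNA, which the SAP's primary model adjusts for: a cheap improvement with a modest possible gain in precision

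*SAP*

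**What the plan says.** **Primary efficacy model (SAP 7.1.3.1).** The log10 change in HIV-1 RNA "will be fitted in a mixed-effects linear model by treatment, with baseline plasma HIV-1 RNA" among the fixed effects, separately for each part. The example code reads "model chgRNA = baseRNA visit dose".

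**Dose-response model (SAP 10.1 and 10.1.4.1).** "To model the dose-response relationship, a frequentist simplified Emax model is planned". The parts are pooled: "Part 1 and Part 2 doses combined in the model fitting", and again "The statistical model will use doses from both parts for model fitting". The code's prediction line begins "PRED = E0 +(EMAX-E0)/(1+(ED50/DOSE". It has no baseline viral load and no term for part.

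**Exposure-response model (SAP 11.1.3).** "To model the exposure-response relationship, a frequentist three-parameter E_{max} model is planned". It has the same form, with a PK parameter and EC50 in place of dose and ED50. SAP 11.1.2 drops the Part 1 RNA values from Days 9 to 11 so that both parts can enter one model. E0 here is the response at zero exposure, not baseline viral load.

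The linear fallback models in both sections also omit baseline. The SAP gives no reason for treating the covariate differently from section 7.1.3.1.

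**The concern.** The primary model compares arms within a part, where randomisation protects the comparison. The pooled curves compare 10 and 200 mg (Part 1) with 40, 80 and 140 mg (Part 2), so dose is tied to part. The parts were randomised separately and at different times. Protocol 6.1 criterion 10, on starting cART on Day 8, fits only Part 2; Part 1 participants waited until after final follow-up (Protocol 5.1.1.2). The dose-response fit uses the Per Protocol population (SAP 10.1.3), and exposure within a dose is not randomised at all. Similar baselines along the curve are therefore an assumption.

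There is also a reason in the documents why the change may depend on baseline: a participant who starts low has less room to fall before reaching the detection limit.

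At stake is the precision of Emax and ED50 or EC50. Exposure-response is a secondary objective, Protocol 10.3.2.2 relies on both parts together for the dose-exposure-response curve, and Protocol 3.1 says the study's data will inform Phase 2b doses.

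**Working it through.** **Inputs from the documents.** SD of the maximum log10 change 0.4 and n = 6 per dose (Protocol 10.1.1); the five doses and 2 placebo participants per part (SAP 2.3); screening RNA at least 5000 copies/mL (Protocol 6.1); values below the limit set to 49 copies/mL for summary tables (SAP 7).

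**Assumed, not in the documents.** Emax 2.0 log10, ED50 11 mg, baseline SD 0.5 log10, correlation ρ between baseline and change from 0 to 0.7, placebo included in the fit.

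**The plan's own figure.** No precision target is given for the Emax models. The nearest sample-size figure is Protocol Table 5, with 81.8% at a true mean drop of 1.3 log10. Simulating with SD 0.4, n = 6 and the stated priors gives 81.6%, so the SD is used here as the protocol uses it.

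**Precision.** If baseline acts additively, the residual SD falls by the factor √(1 − ρ²), less a small cost for one extra parameter. At ρ = 0.5, √(1 − 0.25) = 0.866. Simulated trials fitted with and without the mean-centred baseline term gave these ratios of SD (with ÷ without):

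| ρ | Emax | ln ED50 | Effect at 100 mg |
|---|---|---|---|
| 0 | 1.03 | 1.02 | 1.01 |
| 0.3 | 1.00 | 0.97 | 1.00 |
| 0.5 | 0.89 | 0.88 | 0.97 |
| 0.7 | 0.78 | 0.74 | 0.92 |

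A further run of 700 trials per setting let baseline act on Emax instead, both in generating the data and in the fit. At ρ = 0.5 it gave ratios of 0.92 to 0.96 for Emax and 0.93 to 0.95 for ln ED50. Across the two forms, the gain at ρ = 0.5 is about 4-12%. In sample-size terms that is 1/0.96² = 1.09 to 1/0.89² = 1.26 for Emax.

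**Baseline gap between parts.** The chance difference in mean baseline between 12 and 18 active participants has SD 0.5 × √(1/12 + 1/18) = 0.19 log10. Take a larger gap of 0.5 log10 with ρ = 0.5. The slope on baseline is 0.5 × 0.4/0.5 = 0.4, so the parts are offset by 0.4 × 0.5 = 0.20 log10. The fits then give:

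- Emax 2.17 unadjusted and 2.12 adjusted.
- Effect at 100 mg 1.94 and 1.92 log10.
- Median ED50 11.3 and 9.9 mg.

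The mean baseline shift over all 34 is 0.5 × 20/34 = 0.294, so the true effect at 100 mg at mean baseline is 2.0 × 100/111 + 0.4 × 0.294 = 1.80 + 0.12 = 1.92. The adjusted fit recovers this and the unadjusted fit is 0.02 too high. The mid-range effect barely moves because the Part 2 doses lie between the Part 1 doses. The adjusted ED50 is no closer to the assumed 11 mg: a curve forced through zero cannot absorb an additive shift except through its shape.

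**Floor.** From 5000 copies/mL to the imputed 49, the largest observable fall is log10(5000/49) = 2.01.

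These runs cover the dose-response model only. No size was worked out for EC50.

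**The case against.** The strongest reply is that these are exploratory curves. The SAP states that "No formal hypotheses will be tested", exposure-response is explored with several Emax models compared by AIC, and sections 10.1.4.1 and 11.1.3 allow data-driven adjustment. A simple Emax model described the prior compound's results (Protocol 5.5.1), with no baseline term mentioned. With about 30 active participants at five doses, few parameters is a defensible choice, and the covariate list of a within-part linear model does not bind a pooled nonlinear one.

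This limits the weight of the point but does not remove it. The general allowance for adjustment names no covariate, and the sponsor is unblinded, so naming baseline in advance has value.

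Three stronger readings are tempting, and the documents do not support them:

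- *Precision is certainly lost.* That needs a correlation of roughly 0.45 or more, and no correlation is given.
- *The pooled curve is materially biased by baseline differences between parts.* Subtracting baseline already removes differences in level. Only the dependence of the change on baseline remains, and its effect at mid-range doses is about 0.02 log10 even for a large gap. Adjustment would not remove other differences between parts, such as calendar time.
- *Baseline adjustment solves the floor, with a cap of 2.10 log10.* That figure uses the protocol's 40-copy assay limit (Protocol 9.1.1). Under the SAP's imputation the cap is 2.01. The 5000-copy limit also applies at screening, not on Day 1. A floor is a censoring problem, which a linear baseline term does not model.

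**Conclusion.** The omission is real and unexplained: the SAP adjusts the change in HIV-1 RNA for baseline within each part, then drops the covariate in the two models that pool separately randomised parts. The consequence is a possible, modest loss of precision. At an assumed correlation of 0.5 it is about 4-12% of the SE of Emax and ln ED50; at 0.7 the additive form gives 22-26%. It is almost nothing at 0.3, and at zero correlation adjustment would cost 1-3%. Bias between parts is small.

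These sizes rest on the protocol's SD of 0.4 and on assumed values for Emax, ED50, baseline SD and correlation. This is a minor point: a cheap improvement, not an error that undermines the analysis.

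**What to change.** In SAP 10.1.4.1 and 11.1.3, prespecify an Emax fit with mean-centred baseline log10 HIV-1 RNA as a covariate. Tabulate the curve at mean baseline and report it beside the planned unadjusted fit.

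State in advance which form is used:

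- additive, as in 7.1.3.1: E0 + Emax × Dose/(ED50 + Dose) + b × (baseline − mean); or
- on the maximum: (Emax + b × (baseline − mean)) × Dose/(ED50 + Dose).

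Use the PK parameter and EC50 in the same way in 11.1.3. The additive form sits better in a model with E0. The section 10.1.4.1 equation has no E0 while its example code does, so that mismatch should be settled at the same time.

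The cost is one extra parameter with about 30 active participants, an SE wider by about 1-3% if baseline is unrelated to response, and one more term in the code. Baseline HIV-1 RNA is already collected.

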2.3. Study Design

Overview of Study Design and Key Features	

The diagram illustrates the study design, divided into Part 1 and Part 2. Part 1 starts with N=14 participants randomized on Day 1. They are assigned to three groups: GSK3640254 200 mg once daily (N=6), GSK3640254 10 mg once daily (N=6), and PLACEBO (N=2). Part 2 starts with N=20 participants randomized on Day 1. They are assigned to four groups: GSK3640254 Dose 90% Max Effect 140 mg (N=6), GSK3640254 Dose 75% Max Effect 80 mg (N=6), GSK3640254 Dose 30% Max Effect 40 mg (N=6), and PLACEBO (N=2). An unblinded interim analysis is conducted by the Study Team to confirm GO to Part 2 and refine Part 2 doses as needed. The timeline shows Day 1 Randomization, Follow-up at Day 10 for Part 1, and Day 1 Randomization, Follow-up at Day 7 for Part 2.
	
Design Features	
 This is a Phase 2a, global, multicentre, randomized, double-blind (Sponsor-unblinded), placebo-controlled, adaptive clinical trial to evaluate the antiviral effect, safety, tolerability and PK/ pharmacodynamics (PD) of GSK3640254 over 10 days in study Part 1 and over 7 days in study Part 2 in ART naïve HIV-1 infected adults, who are termed “participants” in the study. All participants will be screened for eligibility before being randomized, preferably within 14 days, into a 10-day treatment period in Part 1 and into a 7-day treatment in Part 2. The 14-day screening period may be extended to 28 days in some cases to allow receipt of all screening results and/or to accommodate scheduling.
Dosing	
 Part 1 will include approximately 14 randomized participants and will evaluate two active doses of GSK3640254, 200 mg once daily or 10 mg once daily, in cohorts of 6 participants each for 10 days. A cohort of 2 participants will be randomized to receive placebo for 10 days. Part 2 will include approximately 20 randomized participants and will evaluate three active doses of GSK3640254, 140/80/40 mg once daily, in cohorts of 6 participants each for 7 days. A cohort of 2 participants will be randomized to receive placebo for 7 days.
Time & Events	
 See Appendix 2: Schedule of Activities for additional details of activities
Treatment Assignment	
 All participants will be centrally randomized using an Interactive Voice/Web Response System (IVRS/IWRS).

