10.1.2. Summary Measure

- Parameter estimates for Emax, ED50 and variance along with their standard error, and 95% CI

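### The SAP does not name the interval method for ED50 and EC50, and its example code gives symmetric intervals whose upper limit falls short about two to three times too often

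*SAP*

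**What the plan says.** SAP 10.1.2 lists the dose-response summary as "Parameter estimates for Emax, ED50 and variance along with their standard error, and 95% CI". SAP 10.1.4.1 repeats this ("estimates Emax, ED50 and Variance along with their standard error, and 95% CI"), and SAP 11.1.3 has the matching line for exposure-response: "estimates E0, Emax, EC50 and Variance along with their standard error, and 95% CI". None of the three names a method for the interval.

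The only technical specification is the example PROC NLMIXED code. It declares ED50 and EC50 directly as parameters, with the constraints "BOUNDS E0>0 EMAX>0 ED50>0 S2E>0" and "BOUNDS E0>0 EMAX>0 EC50>0 S2E>0". There is no log parameterisation, profile likelihood or bootstrap. Both sections allow adjustments in the light of the data, but do not say which.

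SAP 2.3 gives the design: "two active doses of GSK3640254, 200 mg once daily or 10 mg once daily, in cohorts of 6 participants each for 10 days" in Part 1 and "three active doses of GSK3640254, 140/80/40 mg once daily, in cohorts of 6 participants each for 7 days" in Part 2. For the dose-response fit, "The statistical model will use doses from both parts for model fitting", which makes 30 participants on active drug.

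**The concern.** Run as written, the code gives a Wald interval on the mg (or ng/mL) scale: estimate ± t × SE, with the maximum-likelihood variance RSS/n. The bound ED50>0 restricts the estimate. It does not restrict the confidence limits.

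That interval suits an estimate with a roughly symmetric distribution, which this one does not have. At an ED50 near 11 mg, the 10 mg arm sits at about 48% of Emax and the next arm, 40 mg, already at about 78%. Six participants therefore carry most of the information on ED50, and the estimate is right-skewed. When it comes out low, its SE is small too, so the interval is short and can lie wholly below the truth. When it comes out high, the SE is large and the interval covers easily. The misses therefore pile up on one side.

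Protocol 3.1 says the data will guide Phase 2b dose selection. An upper limit that is too low makes the potency estimate look more precise than it is, and a negative lower limit for a dose has no meaning.

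**Working it through.** **Inputs**
- SD of the log10 maximum drop: 0.4 (protocol 10.1.1).
- Doses and n: 10/40/80/140/200 mg, 6 each (SAP 2.3), so n = 30.
- ED50: solving median % = 100 × dose/(dose + ED50) on protocol Table 1 gives 5 × 68.6/31.4 = 10.9 mg at the 5 mg row and 200 × 5.4/94.6 = 11.4 mg at the 200 mg row. I use 11 mg.
- Emax: not stated. Assumed 1.3 to 2.0 log10, from the 1.3 cut-point and the top of the simulated range in protocol 10.1.1.
- Model: the two-parameter equation in the text of SAP 10.1.4.1.

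**Reproducing the plan's own figure.** The documents give no coverage figure, so I checked SD and n on protocol Table 5. With a flat prior and known SD, the chance that the sample mean exceeds 1.3 − 0.8416 × 0.4/√6, when the true mean is 1.3, is 80.0%. The table gives 81.8%. For n = 8 it is 80.0% against 81.3% in Table 6. All rows from 0.8 to 1.6 agree within 2 points.

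**Large-sample SE of ED50.** Let x = d/(d + 11) and g = d/(d + 11)². Over the five doses, Σx² = 3.3728, Σxg = 0.0413 and Σg² = 0.000902.

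S = Σg² − (Σxg)²/Σx² = 0.000902 − 0.000506 = 0.000396

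SE = 0.4/(Emax × √(6S)) = 0.4/(Emax × 0.0487)

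This is 6.3 mg at Emax 1.3, 5.5 mg at 1.5 and 4.1 mg at 2.0. With t(30 df) = 2.042, an estimate exactly on target at Emax 1.5 has limits 11 ± 11.2, or −0.2 to 22.2 mg. About half of trials should then give a negative lower limit. Dividing by n rather than n − 2 shortens the SE by only 1 − √(28/30) = 3.4%, so skewness is the main cause.

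**Simulated Wald interval for ED50** (20,000 trials per row; nominal miss 2.5% per side)

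| Emax | True ED50 above upper limit | True ED50 below lower limit | Coverage | Lower limit < 0 |
|---|---|---|---|---|
| 1.3 | 8.0% | 0.1% | 92.0% | 75% |
| 1.5 | 7.5% | 0.1% | 92.4% | 48% |
| 2.0 | 6.4% | 0.4% | 93.2% | 5% |

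The upper-side miss is 3.2, 3.0 and 2.6 times nominal. Over ED50 5-40 mg it is 4.9-11.0%.

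**F-based profile-likelihood interval** (6,000 trials per row). It keeps every ED50 with RSS ≤ RSSmin × (1 + F/28), where F(0.95; 1, 28) = 2.048² = 4.19.

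| Emax | Miss above | Miss below | Median upper limit, profile | Median upper limit, Wald |
|---|---|---|---|---|
| 1.3 | 2.4% | 2.8% | 33.1 mg | 23.1 mg |
| 1.5 | 2.6% | 2.8% | 28.8 mg | 21.7 mg |
| 1.7 | 2.7% | 2.7% | 25.7 mg | 20.4 mg |
| 2.0 | 2.5% | 2.2% | 22.5 mg | 18.9 mg |

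The median point estimate is 11.0-11.1 mg in every row.

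**Log-scale Wald limits, back-transformed:** always positive, with misses of 0.1-1.1% above and 3.2-3.3% below.

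**EC50, indicative only.** Take EC50 = 1.93 × 19.1 = 36.9 ng/mL (protocol 5.5.1), an assumed exposure CV of 30-50%, and the reduced model without E0. The upper-side miss is then 6.2-7.3% and the lower-side miss 0.1-0.8%. SAP 11.1.3 starts from three parameters, so these are not the plan's operating characteristics. A three-parameter dose-response fit with 4 placebo participants gave an upper-side miss of 8.1-10.8% for ED50, again in the same direction.

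**The case against.** **The Wald form is inferred.** The SAP text never names it, the code is labelled as an example, and adjustment is allowed. That stands: strictly, the defect is that no method is named and the default is symmetric. An unspecified adjustment does not supply a method, though.

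**Coverage is close to nominal, and nothing is tested.** Both are true. SAP 2.4 rules out formal hypotheses, and protocol 10.3.3.1 calls the dose and exposure relationships exploratory. The fault is tail imbalance and impossible limits, not a collapse of coverage.

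**ED50 of 11 mg predates Part 1.** After the interim analysis the Part 2 doses became 40/80/140 mg, so the true value may differ. The size would then change, but the Wald interval stays one-sided across the ED50 range examined.

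A reader might also infer more than the documents support:
- That Tables 5.1 and 6.1 hold the only interval estimates of response. Figures 2.1 and 2.2 plan t-based 95% intervals for mean viral load change by treatment.
- That the dose needed will look smaller. The point estimate does not shift, ED50 is not the target dose, and no decision rule uses its confidence limit.
- That negative limits will be common. That depends on an Emax the documents never give.
- That the variance divisor should change in every interval. The problem shown here is confined to ED50 and EC50.

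**Conclusion.** The point holds as a fault in specification with a measurable effect. As coded, the ED50 interval puts nearly all its misses on one side: the upper limit is too low in about 6-8% of trials, against 2.5% nominal. Typically it sits 4 to 10 mg below the profile limit (18.9 against 22.5 mg at Emax 2.0; 23.1 against 33.1 mg at Emax 1.3). This rests on ED50 near 11 mg, SD 0.4, the two-parameter model, Emax between 1.3 and 2.0, and the code being run with its default limits. For EC50 the direction is well supported, but the size is not fixed by the documents. In an estimation-only analysis the interval is the main statement of uncertainty, so the change is worth making. It is not critical to the trial.

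**What to change.** In SAP 10.1.2, 10.1.4.1 and 11.1.3, state that the 95% limits for ED50 and EC50 are profile-likelihood limits, F-based, with the residual variance for these limits on n − p degrees of freedom. Add that an upper limit that does not close is reported as not estimable.

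The simpler alternative is to estimate log(ED50) and log(EC50) and exponentiate their limits. The limits themselves must be transformed: asking the procedure for an estimate of exp(log ED50) would bring back a symmetric interval. This version is somewhat conservative on the upper side, so the profile interval is preferable.

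The cost is a sentence in each section and a few lines of code. No data, endpoint or point estimate changes. The downside is that reported upper limits will be wider.

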7.1. Primary Efficacy Analyses

7.1.1. Endpoint / Variables

- Change from baseline to the nadir (maximum change from baseline) in Plasma HIV-1 RNA
- Change from baseline to Visit 6 (Day 11 in Part 1 and Day 8 in Part 2) in Plasma HIV-1 RNA

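### The example code for the Emax models does not match the stated models: an extra E0 in SAP 10.1.4.1, a different Emax in 11.1.3, and positive bounds on a response whose sign is never stated

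*SAP*

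**What the plan says.** **Dose-response (SAP 10.1.4.1).** The text says that "a frequentist simplified Emax model is planned", and the displayed equation is `Emax/(1 + ED50/Dose)` plus error, with no E0. The results table is to hold Emax, ED50 and the variance. The response "is the change from baseline, defined as Log10 Maximum change from baseline to Day 8", and the section adds: "The observed maximum change from baseline in Plasma HIV-1 RNA will be used as the response variable in the Emax model". SAP 7.1.1 fixes what maximum change means: "Change from baseline to the nadir (maximum change from baseline) in Plasma HIV-1 RNA". No sentence reverses the sign.

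The example code in the same section has the bounds "BOUNDS E0>0 EMAX>0 ED50>0 S2E>0", and its prediction line begins "PRED = E0 +(EMAX-E0)/(1+(ED50/DOSE". It therefore carries an E0 that the equation and the table lack.

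**Exposure-response (SAP 11.1.3).** The displayed equation is `E0 + Emax/(1 + EC50/PK)`. The code's prediction line begins "PRED = E0 +(EMAX-E0)/(1+(EC50/PARAM", with bounds "BOUNDS E0>0 EMAX>0 EC50>0 S2E>0". A non-significant E0 is to be dropped from the final model. Section 10 has no such rule.

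**Model choice.** SAP 10.1 and 11.1.1 select by lowest AIC. Both sections offer a linear fallback through the origin, whose slope carries no sign bound.

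**The concern.** The code is the only place where the SAP says how these models will be fitted, and it differs from the text in three ways.

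1. The dose-response code estimates a parameter that the stated model does not contain. This changes what ED50 means and how well it is estimated.
2. A fall in viral load is a negative change from baseline, yet E0 and EMAX are constrained to be positive.
3. In the exposure-response model the same name, Emax, stands for two different quantities.

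Protocol 3.1 says that the study's data will be used to select Phase 2b doses. Emax, ED50 and EC50 are the summaries of dose-response and exposure-response that this modelling reports, so a reader should know which model produced them.

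**Working it through.** The documents give no numerical output for these models, so there is no planned figure to reproduce.

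**Inputs**
- Doses 10, 40, 80, 140 and 200 mg, six participants each (SAP 2.3).
- SD 0.4 log10 (protocol 10.1.1).
- ED50 about 11 mg. Fitting `100/(1 + ED50/Dose)` to the ten medians in protocol Table 1 gives 11.1 mg and matches all of them within 0.43 points (10 mg: 47.3 against 47.6; 200 mg: 94.7 against 94.6).
- Assumed: Emax of 1.7 or 2.0 log10 (the protocol simulates true mean drops from 0.5 to 2) and E0 from 0 to 0.3. Placebo is left out.

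**Step 1: sign.** Put w = 1/(1 + ED50/Dose), which lies between 0 and 1. The code predicts E0(1 − w) + EMAX·w, which cannot be negative when both parameters are bounded below by zero. If every response is negative, the closest feasible prediction is zero. Then E0 = EMAX = 0, ED50 drops out, and the variance becomes the mean of y².

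Noise-free, with Emax 2.0 and ED50 11, the declines are 0.952, 1.569, 1.758, 1.854 and 1.896. Their squares sum to 13.491, so the variance is 13.491/5 = 2.698. With Emax 1.7 and SD 0.4 it is 0.85² × 2.698 + 0.16 = 2.11, a residual SD of 1.45 instead of 0.4. All 600 simulated fits at Emax 2.0 collapsed to zero in this way (largest estimate about 2 × 10⁻¹³).

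**Step 2: what AIC then does.** The line through the origin has residual sum of squares Σy² − (ΣDy)²/ΣD², which is below the Σy² of the collapsed fit. In the noise-free case its mean square is (13.491 − 851.7²/67,700)/5 = 0.555, against 2.698. It also has two parameters against four, so its AIC is always lower. In simulation the bounded code lost to the line in 400 of 400 trials, and the text's Emax model never did.

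**Step 3: the extra E0, with the response coded as a positive decline.** Noise-free, asymptote 2.0, ED50 11:

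| True E0 | Text: Emax, ED50 | Code: EMAX, ED50 |
|---|---|---|
| 0 | 2.00, 11.0 | 2.00, 11.0 |
| 0.1 | 1.99, 9.9 | 2.00, 11.0 |
| 0.2 | 1.98, 8.9 | 2.00, 11.0 |
| 0.3 | 1.98, 8.0 | 2.00, 11.0 |

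The two ED50s are different quantities once E0 exceeds zero. With E0 = 0.2, half of EMAX is 1.0. Solving 0.2 + 1.8/(1 + 11/D) = 1.0 gives 11/D = 1.25, so D = 8.8 mg. The code's 11.0 is the dose halfway between E0 and EMAX, not the dose giving half the maximum.

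With SD 0.4 and true E0 = 0, separate simulation runs gave:

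| Assumed Emax | Text ED50, median (90th percentile) | Code ED50, median (90th percentile) | E0 at its bound |
|---|---|---|---|
| 1.7 | 11.4 (18.3) | 15.8 (85) | about half |
| 1.7 | 11.2 (18) | 14.4 (87) | 55% |
| 1.7 and 2.0 | 11.3–11.5 (18–19) | 15.5 (58–73) | 52–56% |
| 2.0 | 10.6 (quartiles 8.4–13.2) | 14.7 (quartiles 10.1–33.7) | 53% |

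In the last run the two ED50s differed by more than 10% in 45% of trials.

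**Step 4: Emax in SAP 11.1.3.** The text's curve tends to E0 + Emax at high exposure and the code's tends to EMAX. Hence EMAX(code) = E0 + Emax(text). With E0 = 0.2 and Emax 1.8 in the equation, the code prints 2.0.

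**The case against.** The strongest reply concerns the sign. Protocol 10.3.3.1 names the pharmacodynamic measure for these models as a log10 reduction, which is positive. SAP 2.1 says that the protocol's analysis is unchanged. SAP Figure 5.1 and Tables 2.19 and 2.20 speak of a decline. Under that convention the bounds are feasible. This stands. A reader might infer that the planned analysis will return Emax = 0 and show no dose-response. The documents do not support that: the collapse follows only if the variable is entered as 10.1.4.1 defines it. Even then the SAP has a linear fallback. That fallback would not repair the problem, because it would report a straight line where the planning model saturates.

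A second inference is that Emax is mislabelled in 10.1.4.1. It is not: that section calls Emax the maximum response, and the code's asymptote is that quantity. There it is the ED50 label that fails when E0 is above zero. The mismatch over Emax belongs to 11.1.3, where the equation makes it an increment.

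Third, 11.1.3 already drops a non-significant E0. With true E0 = 0, E0 reached 5% significance in about 3% of simulated trials, so the Emax discrepancy would then usually vanish. This stands for 11.1.3 only.

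Fourth, the ED50 shift is the cost of an unneeded parameter when true E0 is zero. If E0 is truly above zero, the code's form fits better. This also stands: the defect is that text and code disagree, not that the code's equation is wrong in itself.

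Finally, the code is headed as an example, adjustments are allowed, and the modelling is exploratory with no formal hypotheses. That makes a wrong output a risk and not a certainty. It does not say which version governs.

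**Conclusion.** The point holds as a mismatch between stated models and code, and should be corrected before the models are run.

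- **SAP 10.1.4.1, equation.** The code adds an E0 that is absent from the equation and the table. With true E0 = 0, the median ED50 moves from about 11 mg to 14–16 mg and the 90th percentile from about 18 mg to about 60–90 mg. In about half of fits E0 is at its bound and the models coincide. The size rests on the assumed Emax of 1.7 (similar at 2.0), ED50 of 11 mg, SD 0.4, six per dose and no placebo data.
- **Sign, both sections.** The response as defined and the bounds contradict each other unless the sign is reversed, and no sentence reverses it. The collapse to zero on negative data is algebra and needs none of these assumptions, but it is conditional on that coding.
- **SAP 11.1.3.** The tabulated Emax differs from the equation's Emax by exactly E0 whenever E0 is kept.

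The protocol says that study data will inform Phase 2b doses. It does not say that these parameters alone will decide them, so the consequence should not be put higher than that.

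**What to change.** - In SAP 10.1.4.1 and 11.1.3, state that the response is decline: baseline minus on-treatment log10 HIV-1 RNA, positive for a reduction.
- In 10.1.4.1, use `PRED = EMAX/(1+ED50/DOSE)` and remove E0 from the parameter and bounds lines.
- In 11.1.3, use `PRED = E0 + EMAX/(1+EC50/PARAM)` and define Emax in words as the increment over E0.
- Keep the remaining bounds consistent with that sign. Whether to remove the E0>0 bound in 11.1.3 is optional. Without it, a small rise at zero exposure can be fitted; keeping it is a modelling preference.

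The cost is a few lines of code and two definitions, with no change to data or design.
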